## Schema

**Statistical Methods:** This study is a prospective single arm Phase II trial to assess the association of BRCA1 protein expression to overall response rate when metastatic breast cancer patients are treated with pegylated liposomal doxorubicin. We plan to consent 50 to 60 patients with the goal of enrolling a total of 50 patients to this study. It is anticipated that 30% of patients will have low BRCA1 protein expression and therefore anticipate approximately a 35 to 15 patient split for intact BRCA1 to low BRCA1 protein expression.

**Definition of primary endpoint:** Response rate is defined as the percentage of evaluable patients who achieve complete response (CR) or partial response (PR) as measured by RECIST 1.1 on CT or PET/CT as the best overall response.

**Definition of secondary endpoints:** Progression free survival will be measured as the times from the start of pegylated liposomal doxorubicin to the time the patient is first recorded as having disease progression or dies. If a patient does not progress or die while being followed via tumor assessment, progression-free survival will be censored at the time of last disease assessment.

### Sample size determination

**Low BRCA1 protein expression:** Since it is expected only 30% of patients will have low BRCA1 protein expression, we will accrue 15 patients to this arm and estimate the response rate among these patients. With a sample size of 15 we will be able to estimate the response rate of 50% in patients with low BRCA1 protein expression with a 95% confidence interval width of  $\pm 25\%$ .

**Normal BRCA1 protein expression:** A Simon two-stage design will be used in which a 10% response rate is considered not promising, a 30% response rate is considered promising, and the probabilities of a type I error (falsely accepting a non-promising therapy) and type II error

(falsely rejecting a promising therapy) are set at 0.10 and 0.10, respectively. In this scenario, the maximum trial size would be 35 patients. In the first stage of this design, 12 patients with intact BRCA1 expression will be accrued. If at least two responses are observed among these 12 patients, then an additional 23 patients will be accrued to the second stage. If 0 or 1 response is observed among the initial 12 patients, then accrual to this cohort will be terminated and declared negative. At the end of the study if 6 or more patients in this cohort respond then pegylated liposomal doxorubicin will be considered worthy of further study in this cohort. This design yields at least 90% probability of a positive result if the true response rate is at least 30% and a 90% probability of a negative result if the true response rate is 10%.

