### **Methodology:**

**IHC staining for BRCA1:** Tumor samples will be reviewed to confirm adequate sample for staining. Tissues sections will be stained for BRCA1 by Genscript A00490 Rb polyclonal clone antibody using the Benchmark Ultra automated stainer (Ventana Medical Systems Inc, Tucson, Arizona). Low BRCA1 protein expression will be defined as  $\leq 5\%$  of cells staining with 1+ intensity of the tumor nucleus (i.e. nuclear long score  $\leq 5$ ). Intact BRCA1 protein expression will be defined as  $\geq 10\%$  of cells staining with 1+ intensity or  $\geq 5\%$  of cells staining with 2+ intensity of their nucleus (i.e. nuclear long score of  $\geq 10$ ). Nuclear long score of 6-9 i.e. 5-10% of cells staining with 1+ or  $< 5\%$  of cells stain with 2+ intensity, will be defined as indeterminate status.

**Quantitation of IHC:** Two Board Certified pathologists ([name], PhD and [name]) will evaluate each case using a semi quantitative histologic scoring method as previously described. Briefly, staining intensity for neoplastic cell's nucleus will be scored as: 0 negative, 1 weak, 2 moderate and 3 intense. In addition,

the percentage of positive neoplastic cells will be evaluated. The overall scores will be calculated by multiplying the intensity by the corresponding percentage of positive cells, resulting in a values ranging from 0 to 300. Low BRCA1 protein expression will be defined as nuclear long score of  $\leq 5$ , intact BRCA1 as nuclear long score of  $\geq 10$ , indeterminate BRCA1 expression as nuclear long score of 6-9.

**Chemotherapy agent:** Pegylated liposomal doxorubicin is frequently used in the salvage treatment of patients with metastatic breast cancer. It is a DNA damaging chemotherapy agent which has been reported to have a 25% overall response rate and 2.5 months median progression free survival in the salvage treatment of metastatic breast cancer. It has been shown to be safe in patients who have received prior anthracycline treatment.

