## 8. Study Statistics

8.1. **Statistical Methods:** This study is a prospective single arm Phase II trial to assess association of BRCA1 protein expression with overall response rate in patients with metastatic breast cancer on pegylated liposomal doxorubicin in patients with metastatic breast cancer. We plan to consent 50 to 60 patients with the goal of enrolling a total of 50 patients, with adequate primary tumor tissue for BRCA1 protein expression, into this study. It is estimated that 30% of patients will have low BRCA1 protein expression and therefore anticipate approximately a 35 to 15 patient split for normal BRCA1 to low BRCA1 expression status.

Recruitment and tissue analysis: Patients will be consented and after enrollment of the first 12 patients, a batch analysis of their tumors will be performed to analyze tumor BRCA1 protein expression. This will allow us to assign the patients to their respective cohorts (Normal BRCA1 protein expression and Low BRCA1 protein expression). This will be done until we have 12 patients in the normal BRCA1 protein arm. After that, an interim analysis will be performed for the normal BRCA1 arm and stopping rule will be applied as mentioned in the study design

8.2. **Analytic plan for primary objective:**

**Definition of primary endpoint:** Response rate is defined as the percentage of evaluable patients who achieve complete response (CR) or partial response (PR) as measured by RECIST on imaging as the best overall response.

**Low BRCA1 protein expression:** The number and percentage of patients falling into response category will be tabulated. The estimate of the response rate will be presented with 2-sided 95% exact binomial confidence intervals. We anticipate this data to be hypothesis generating and will form the basis for a future prospective clinical trial enrolling larger number patients to evaluate if low BRCA1 expression, as determined by IHC, is predictive of response to treatment with DNA damaging agents.

**Normal BRCA1 protein expression:** The estimate of the response rate will be presented with 2-sided 95% exact binomial confidence intervals. If 5 or fewer patients with response are observed among the 35 patients, then there will be no further investigation of the treatment. If 6 responses are observed out of 35 patients, there is 80% confidence that the true response rate >11.2%.

Interim analysis:

**Low BRCA1 protein expression:** No interim analysis will be conducted

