**Process to implement study closure when significant risks or benefits are identified:** Stopping rules will be based on Simon's optimal design (Simon, R. "Optimal Two-Stage Design for Phase II Clinical Trials". Controlled Clinical Trials, 101-10, 1989, Elsevier Science Publishing Company, N.Y., N.Y.) which minimizes the expected sample size under the null response rate. In the patients with normal BRCA1 protein expression if at least two responses are observed among these 12 patients, then an additional 23 patients will be accrued to the second stage. If 0 or 1 response is observed among the initial 12 patients, then accrual to this cohort will be terminated and declared negative. At the end of the study if 6 or more patients in this cohort respond then pegylated liposomal doxorubicin will be considered worthy of further study in this cohort. This design yields at least 90% probability of a positive result if the true response rate is at least 30% and a 90% probability of a negative result if the true response rate is 10%.

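### The only go/no-go rule sits in the normal-BRCA1 cohort and cannot test the BRCA1 hypothesis, yet its negative verdict is worded as ending investigation of the drug altogether

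*Combined protocol and SAP*

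**What the plan says.** Section 2 and the synopsis set the primary objective as a contrast: does low BRCA1 expression have a preferential effect on response?

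The formal rule concerns the normal (intact) BRCA1 cohort only. Under Sample size determination in the synopsis, "a 10% response rate is considered not promising, a 30% response rate is considered promising", and the type I and II error probabilities "are set at 0.10 and 0.10, respectively". "In the first stage of this design, 12 patients with intact BRCA1 expression will be accrued"; with 0 or 1 response the cohort closes, and otherwise it continues to 35.

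The two verdicts are worded differently:

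- Positive (synopsis, Sample size determination, and Section 9, study closure): "if 6 or more patients in this cohort respond then pegylated liposomal doxorubicin will be considered worthy of further study in this cohort".
- Negative at the final analysis (synopsis, Analytic plan for primary objective, and Section 8.2): "If 5 or fewer patients with response are observed among the 35 patients, then there will be no further investigation of the treatment".

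The low-BRCA1 cohort gets a response rate with an exact 95% interval, no threshold and no interim analysis. Its data are called hypothesis generating and are meant to underpin a larger trial. Section 8.2 adds that low-BRCA1 patients will still be enrolled if the normal arm closes. No difference, test or interval comparing response between the cohorts is specified.

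**The concern.** There are two linked problems.

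First, the rule and the objective do not meet. A Simon verdict says whether response in normal-BRCA1 patients looks nearer 10% or 30%. It says nothing about whether low-BRCA1 patients respond better, because the low cohort does not enter it.

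Second, the consequence attached to a negative final verdict is worded too widely. If low BRCA1 marks sensitivity to the drug, a poor response in normal-BRCA1 patients is the expected finding. Read literally, the final-analysis sentence then stops work on the drug, although the same section plans a larger low-BRCA1 trial.

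At stake is how the trial's one formal result is read. A negative normal cohort could be cited against the drug in everyone. It could also be cited in support of BRCA1, although it occurs fairly often when BRCA1 has no effect. The plan rules out neither reading.

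**Working it through.** **Inputs**

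- Simon boundaries: stop if 1 or fewer of 12 respond; negative if 5 or fewer of 35 (synopsis, Sample size determination; Section 9).
- Response rate of the drug in salvage treatment, not selected by BRCA1: 25% (Section 1.2, Methodology: "reported to have a 25% overall response rate").
- Share with low BRCA1: 30% (synopsis, Statistical Methods; Section 8.1).
- Low-BRCA1 response rate: 50%, used in the plan only to state interval width ("estimate the response rate of 50% in patients with low BRCA1 protein expression").

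**Step 1. Reproduce the plan's figures.** With X₁ responses in 12 and X₂ in the next 23,

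P(positive) = Σ over x ≥ 2 of P(X₁ = x) × P(X₂ ≥ 6 − x).

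At 10% this is 9.8%, so P(negative) is 90.2%. At 30% it is 90.1%. Both stated 90% figures are correct. A full search over two-stage designs also returns 1/12, 5/35 as the Simon-optimal design for these rates and errors.

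**Step 2. What normal-cohort rate do the plan's other figures imply?** The plan states none. If the 25% applies to this population and 50% is taken as an expectation,

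0.25 = 0.30 × 0.50 + 0.70 × p, so p = (0.25 − 0.15)/0.70 = 14.3%.

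If BRCA1 has no effect, p = 25%.

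**Step 3. Apply the existing rule at those rates.**

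| True normal rate | Stop at stage 1 | Negative at 35 | Total negative | Positive |
|---|---|---|---|---|
| 10% | 65.9% | 24.3% | 90.2% | 9.8% |
| 14.3% | 47.2% | 23.1% | 70.2% | 29.8% |
| 20% | 27.5% | 12.1% | 39.6% | 60.4% |
| 25% | 15.8% | 4.7% | 20.5% | 79.5% |
| 30% | 8.5% | 1.4% | 9.9% | 90.1% |

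The stage 1 column is (1 − p)¹² + 12p(1 − p)¹¹. At 14.3% that is 0.157 + 0.315 = 0.472.

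**Step 4. Sensitivity to the assumptions in Step 2.**

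- Share 30%, low-BRCA1 response 40%: p = (0.25 − 0.12)/0.70 = 18.6%, P(positive) 53%.
- Share 30%, low-BRCA1 response 60%: p = (0.25 − 0.18)/0.70 = 10.0%, P(positive) 10%.
- Share 15%, low-BRCA1 response 50%: p = (0.25 − 0.075)/0.85 = 20.6%, P(positive) 63%.
- Share 50%, low-BRCA1 response 50%: p = (0.25 − 0.25)/0.50 = 0%, so a positive verdict is impossible.

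The 15% and 50% shares are the ends of the incidence range quoted in the synopsis background. The implied rate is therefore loose, and P(negative) moves with it.

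**Step 5. Compare the wordings.** The stage 1 rule closes accrual to the cohort. The positive verdict applies to the cohort. The low-BRCA1 paragraph looks ahead to a larger trial, and Section 8.2 keeps low-BRCA1 enrolment open after the normal arm closes. Only the final-analysis negative sentence refers to the treatment without restriction. At 14.3% that sentence is reached about 23% of the time, and at 25% about 5%.

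**Step 6. What would address the objective.** The difference in response rates, with an approximate 95% half-width of 1.96 × √[p_L(1 − p_L)/15 + p_N(1 − p_N)/35]. For 50% versus 25% this is 29 points; for 50% versus 14.3% it is 28 points. That is imprecise, but it is an estimate of the contrast in the objective.

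**The case against.** The best defence is context. The unrestricted sentence stands under the normal-BRCA1 heading, the other verdict wordings are limited to that cohort, and low-BRCA1 accrual continues regardless. A careful reader would take the sentence to mean normal-BRCA1 patients. That is probably the intent, but the sentence does not say so, and it is the one that governs the final analysis.

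Simon's 10% and 30% are decision anchors, not forecasts, and the 90% statements are conditional on them. This stands in full. A reader might infer that 30% is impossible in the normal cohort because it exceeds the cited 25% and, with 50% in low BRCA1, implies 0.30 × 0.50 + 0.70 × 0.30 = 36% overall. The documents do not support that: nothing shows that the literature rate carries over to this population, and the plan never states an expected normal-cohort rate.

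A reader might also infer that, if the hypothesis is true, the most likely outcome ends investigation of the drug. That does not follow either. At 14.3% the larger part of the 70% is the stage 1 stop (47%), where the wording is limited to the cohort and low-BRCA1 enrolment goes on.

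Finally, the plan openly calls the low-BRCA1 result hypothesis generating. This is candid, and it is a good reason not to impose a pass mark on 15 patients. It does not supply the comparison that the objective describes.

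**Conclusion.** The point holds as one of wording and interpretation, not of calculation. That the only formal rule cannot answer the primary objective, and that its final negative verdict is worded more widely than the rest of the plan, follows from the text and needs no assumption.

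The size of the problem does rest on assumptions. With 25% overall, a 30% share and 50% in low BRCA1, a negative verdict has about a 70% chance; with no BRCA1 effect and 25% in both cohorts it has 20.5%. A negative verdict is therefore more likely under the hypothesis, but it is common enough without any BRCA1 effect that it should not stand as evidence for one. A positive verdict shows only that normal-BRCA1 response exceeds a 10% benchmark.

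**What to change.** Keep the 12/35 design and its boundaries.

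1. In the synopsis (Analytic plan for primary objective) and Section 8.2, change the consequence of 5 or fewer responses to: *no further investigation in patients with normal BRCA1 expression*. This matches the cohort-limited wording used for the positive verdict.
2. In the same places, state that neither Simon verdict is evidence for or against the BRCA1 hypothesis, and that this question rests on the two cohorts' response rates and their difference with a 95% confidence interval.
3. Optionally, beside the 10% and 30% figures, give the probability of a positive verdict at a true 25% (79.5%).

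The cost is a protocol wording amendment and one added descriptive estimate, with no extra patients and no change to the stopping rule. The interval for the difference will be wide (about ±28 to 29 points at the rates above), in keeping with the hypothesis-generating status that the plan already gives the low-BRCA1 data.

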#### **Analytic plan for primary objective:**

**Low BRCA1 protein expression:** The number and percentage of patients falling into response category will be tabulated. The estimate of the response rate will be presented with 2-sided 95% exact binomial confidence intervals. We anticipate this data to be hypothesis generating and will form the basis for a future prospective clinical trial enrolling larger number patients to evaluate if low BRCA1 expression, as determined by IHC, is predictive of response to treatment with DNA damaging agents.

**Normal BRCA1 protein expression:** The estimate of the response rate will be presented with 2-sided 95% exact binomial confidence intervals. If 5 or fewer patients with response are observed among the 35 patients, then there will be no further investigation of the treatment. If 6 responses are observed out of 35 patients, there is 80% confidence that the true response rate >11.2%.

#### **Analytic plan for secondary objective:**

The progression free survival in patients with low BRCA1 protein expression and intact BRCA1 protein expression will be analyzed by Kaplan-Meier methodology. The results will be summarized by 25th, 50th (median), and 75th percentiles with associated 2-sided 95% confidence intervals,

#### **Interim Analysis**

**Low BRCA1 protein expression:** No interim analysis will be conducted

**Normal BRCA1 protein expression:** An interim analysis for futility will be conducted in this group. The response rate will be used as the endpoint for the interim analysis for this group. The interim analysis will be performed when the first 12 treated patients are accrued. Based on Simon's 2-stage design, if less than 2 responders are observed out of these initial 12 evaluable patients in normal BRCA1 protein expression, patient enrollment will be discontinued into this arm. Otherwise patient enrollment will continue until a total of 35 patients evaluable for response are enrolled. If only 1 response is observed out of 12 patients, there is 80% confidence that the true response rate <22.1%.

**Feasibility Issues:** Patients with metastatic breast cancer (exclude Her-2/neu patients) whose primary tumor tissue is available for assessing defective DNA repair will be identified by the medical oncologists at the University of Arizona Cancer Center and the University of New Mexico to be included and treated with pegylated liposomal doxorubicin in the salvage setting. During the past year we have treated more than 25 patients with metastatic breast cancer with liposomal doxorubicin. We anticipate to complete accrual of 50 patients in 2 years. If we do not

accrue as expected after year 1, we plan to expand enrollment to other institutions we are currently collaborating (University of Washington and University of New Mexico).

## 1. Introduction

### 1.1. Breast Cancer

Breast cancer is a heterogeneous disease with different clinico-pathological features, responses to treatment and prognoses. Progress has been made in the development of targeted therapies (for example HER-2/neu targeting monoclonal antibodies and small molecule inhibitors) that have made a substantial improvement in both response rates and survival. Despite these clinical advances there are still 40,000 women who die in the US of breast cancer each year. Therefore, there is a continuing need to search for additional therapeutic strategies. All patients with metastatic breast cancer eventually receive treatment with chemotherapy. In the available menu of chemotherapy agents, clinicians frequently select therapy based on the patient's treatment history, prior response rates to similar classes of drugs, toxicity profiles, patient preference, etc. Currently, there is no proven clinical predictive marker for selecting the most efficacious chemotherapy agent outside the setting of the targeted therapies i.e. HER2 or ER targeted antitumor agents. Better methods for choosing the most efficacious treatment would spare patients undue toxicity and lead to improved response rates.

### 1.2. Background

It is established that women with germline mutations in breast cancer 1, early onset gene (BRCA1) or breast cancer 2, early onset gene (BRCA2) are at increased risk for developing breast and ovarian cancers. In addition, there is a higher risk for pancreatic, prostate and male breast cancer. This is thought to be related to the roles BRCA1 and BRCA2 genes play in DNA repair. DNA damage activates cell cycle check points and recruitment of DNA repair machinery. In cells deficient in the BRCA1 or BRCA2 genes there is defective DNA repair of double-strand DNA breaks (DSB) through homologous recombination (HR), a conservative DNA repair mechanism with a high degree of fidelity. Alternative error-prone, potentially mutagenic DNA repair mechanisms like non-homologous end joining (NHEJ) and single stranded annealing (SSA) compensate for this loss, but lead to genomic instability. The relative roles of BRCA1 and BRCA2 in repair of DNA DSB have been explored and better defined over the past two decades. BRCA1 is a critical organizing molecule that has been linked to a range of cellular processes beyond DNA repair, including transcriptional regulation and chromatin remodeling. BRCA2 function in HR is primarily via regulation of RAD51 activity. BRCA2 regulates RAD51 recombinase, which is a critical step in strand invasion and homology directed repair.

Germline mutation in one BRCA1 or BRCA2 allele is sufficient to predispose for cancer development. There is a loss of heterozygosity, with loss of the normal allele while retaining the mutant allele, in the tumor tissue of susceptible individuals, suggesting that the genes may have a role as tumor suppressors. Somatic mutations in BRCA1 or BRCA2 do not occur frequently in sporadic (or non-familial) breast cancer but potentially any (somatic) inactivation of the genes could result in phenotypic suppression of BRCA, a phenomenon called "BRCAness" (or more properly "BRCAlessness"). This phenomenon has been reported in sporadic cancers which do not have germline mutations in BRCA1 or BRCA2, but display similar inactivation of the BRCA related genes and consequently have defective HR.

### **Preferential effect of chemotherapy in relation to BRCA1 or BRCA2 expression**

The key roles BRCA1 and BRCA2 genes play in DNA repair are through HR, thus cells deficient in these proteins could be more sensitive to chemotherapy agents which produce DNA damage. DNA injury can be induced by strand breaks through failure to reseat cleavable complexes in strand passage or by intercalation with base pairs (i.e. anthracyclines) or by DNA adduct formation (i.e. alkylators and platinating agents) with subsequent intra- or interstrand DNA crosslinks and resultant double strand breaks. Most published clinical studies assessing homologous recombinant deficiency (HRD) involve BRCA1 signatures and are retrospective.

Rodriguez et al reported higher sensitivity to anthracycline-based therapies in patients whose tumor samples had a defective DNA repair gene signature (determined by quantitative RT-PCR in a 69 gene low density array). In a study with similar design by Lips et al, approximately 50% of triple negative tumors were found to have BRCA1 inactivation (determined by aCGH, mRNA levels, or BRCA1 promoter methylation) but it was only modestly predictive of response. Vollenbergh et al reported association of BRCA1 like signature (determined by aCGH) to be associated with a higher recurrence free survival and overall survival after high dose platinum-based chemotherapy. One reported prospective trial of 28 patients reported higher pathological complete responses after neoadjuvant cisplatin, in patients with BRCA1 mutations, low BRCA1 mRNA levels, or BRCA1-promoter methylation.

DNA damaging chemotherapy can potentially influence expression of BRCA1 protein in treated tumor cells as a potential mechanism of resistance. There is currently only 1 report in the literature assessing change in expression of BRCA1 in primary and metastatic tumors. This was assessed in 9 BRCA1 germline mutation patients with ovarian tumors who were treated with a platinum-containing chemotherapy regimen. Their primary and metastatic tumor specimens were evaluated for BRCA1 mutations by DNA sequencing and BRCA1 protein expression by IHC. Four of the specimens showed reversal of mutations by DNA sequencing however clinical implication of that change was unclear. In addition this data only included patients with germline mutations and not in sporadic tumors which have an acquired loss of BRCA1. Currently, there is no data suggesting that acquired BRCA1 loss can be reversed with treatment. We propose to determine if reversal of BRCA1 protein expression is observed after DNA damaging chemotherapy as a secondary aim.

